#### 2 HYPOTHESIS AND OBJECTIVES

We hypothesize that belantamab mafodotin as maintenance therapy post-CAR-T until progression will be safe, and will prolong progression-free survival (PFS) regardless of the degree of best response after CAR-T

#### 2.1 Primary Objectives

To describe PFS of patients receiving belantamab mafodotin as maintenance (eight weekly) after anti-BCMA CAR-T administration for relapsed/refractory myeloma.

#### 2.2 Primary Endpoint

1. Twelve-month conditional progression-free survival (PFS), defined as the probability of being alive without progression/relapse or death at 12 months from the time of CAR-T administration conditional on being alive without progression/relapse at 3 months from the time of CAR-T. Follow-up time will be counted from the date of CAR-T cell infusion, left-truncated at the start of study treatment, to the date of first documentation of progression or death due to any cause. Patients last known to be alive and progression-free are censored at date of last contact.

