- 16. NGS for MRD assessment (clonoSEQ®) will be performed on bone marrow aspirate sample. Bone marrow aspiration with MRD assay (first pull, in subjects found to be MRD-informative based on clone identification sample) and flow cytometry/cytotoxicity assays will be performed within seven days before cycle 3 day 1, and cycle 7 day 1 and within seven days before or after cycle 12 day 56. Samples are also to be obtained/sent for correlative studies (refer to Appendix 5).
- 17. Patient-reported outcomes (refer to Appendix) PRO assessments should be completed before any other study procedures are performed (except for blood draws).:
  - a. EORTC-QLQ-MY20 and EORTC QLQ-C30
    - i. Collect at cycle 1 day 1 (prior to treatment), cycle 3 day 1, cycle 7 day 1, cycle 9 day 1, and 70-day safety visit.
  - b. OCULAR SURFACE DISEASE INDEX (OSDI)
    - i. Collect at cycle 1 day 1 (prior to treatment), every cycle day 1, and 70-day safety visit.
- 18. For patients who discontinue treatment prior to progression, continue standard-of-care follow-up every three months until progression or start of another treatment (whichever comes first), then continue to long-term follow-up.
- 19. Long-term survival data collected/reported approximately every six months (+/- 30 days).
- 20. Urine dipstick for protein may be used to assess for presence of urine protein. Albumin/creatinine ratio needs to be done in any participant with urine dipstick result of ≥1+ at screening, or with positive protein if urine dipstick protein quantification is not available.

Short Title: MCW EMBRACE TRIAL 15 Version No.: 3
Version Date: 12/29/2022

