For all subjects, disease evaluations will continue to be performed at least every 56 days (± seven days) until confirmed PD, death, start of a new anti-cancer treatment, withdrawal of consent, or loss to followup, whichever occurs first. Traditional efficacy assessment will be performed every cycle by serum protein electrophoresis and immunofixation and serum-free light chains, and after every two cycles by 24-hour urine protein electrophoresis and immunofixation. Minimal residual disease (MRD) assessment by next generation sequencing (clonoSEQ®), BCMA expression on bone marrow plasma cells and soluble BCMA/BAFF/APRIL will occur at screening and after two, six, and 12 cycles of belantamab mafodotin maintenance (refer to correlative schedule). In case of PD, subjects will be followed to ascertain subsequent anti-cancer therapy, if any, and survival status every six months (± 30 days) until withdrawal of consent, lost to follow-up, death, or the end of the study. Patients who discontinue treatment prior to progression will continue standard-of-care follow-up every three months until progression or start of another treatment (whichever comes first), then they will continue to long-term follow-up.

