#### 5.8 Follow-up Period

For patients who discontinue treatment prior to progression, continue standard-of-care follow-up every three months until progression or start of another treatment (whichever comes first), then continue to long term follow-up.

All patients will be followed for survival and follow-up data every six months (± 30 days) until withdrawal of consent, loss to follow-up, death, or the end of the study, whichever occurs first.

Refer to section above regarding ocular examination and procedures during follow-up.

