#### 8.2 Determination of Sample Size and Accrual Rate

#### 8.2.1 Primary Endpoint

The primary endpoint of the study is the 12-month progression-free survival (PFS) with time counted from the CAR-T infusion conditional on being alive and progression-free at day +90 post CAR-T. An event will be defined as documented progression or death for any cause, subjects without an event will be censored at the last date known to be alive without progression. Left truncation at the time of the start of study treatment will be used to adjust for "immortal time" after day +90 before study enrollment.

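### Section 2.2 censors PFS at last contact although disease evaluation stops at new therapy; 8.2.1 and 8.2.5 give a different date, and no section says how new therapy is handled

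*Combined protocol and SAP*

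**What the plan says.** The plan gives two censoring dates for the same endpoint.

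- Section 2.2: "Patients last known to be alive and progression-free are censored at date of last contact".
- Section 8.2.1: "subjects without an event will be censored at the last date known to be alive without progression". Section 8.2.5 (Primary outcome) repeats this.

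The event in 8.2.1 and 8.2.5 is documented progression or death from any cause. Starting another anti-myeloma therapy is neither an event nor a censoring point in any section, and no sensitivity analysis deals with it.

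Assessment, however, does depend on new therapy. Section 3.1 runs disease evaluations "until confirmed PD, death, start of a new anti-cancer treatment, withdrawal of consent, or loss to followup". For patients who stop study drug before progression, section 5.8 says to "continue standard-of-care follow-up every three months until progression or start of another treatment (whichever comes first"), after which they move to long-term follow-up. That follow-up is described in section 5.8 as "All patients will be followed for survival and follow-up data every six months" and in study calendar footnote 19 as "Long-term survival data collected/reported approximately every six months".

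The plan foresees a switch without progression: calendar footnote 10 lists progression and the start of a subsequent anti-myeloma therapy as separate reasons for treatment to end.

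**The concern.** Once a patient starts a new therapy, no disease evaluation is scheduled, but the patient can still be contacted. If the PFS clock runs to last contact, a living patient who switched at month 8 can still sit in the month-12 risk set as progression-free, with no assessment after the switch. Progressions that would have been seen are lost and the Kaplan-Meier estimate rises.

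The section 8.2.1/8.2.5 wording does not do this if it is read strictly, because progression-free status is no longer known once evaluation stops. It has a different weakness. If patients are switched because they are close to progression, censoring them is informative.

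The primary test compares a single-arm estimate with a fixed 54%, so no control arm shares the bias. With 45 patients and a true PFS of 54%, the expected number of events is 45 × 0.46 = 20.7. A 10% share of those is about two patients.

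**Working it through.** **Inputs from the documents.** Null conditional 12-month PFS 0.54 (8.2.2); alternative 0.74 and n=45 (8.2.3); one-sided 5% z-test on the Kaplan-Meier estimate (8.1); treatment start 90–120 days after CAR-T (3.1), taken as months 3 to 4; exponential PFS (8.2.3).

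**Plan's own figure.** Section 8.2.3 states 84% power. An exact binomial rule requiring at least 31 of 45 progression-free gives alpha 0.031 and power 83.0%. A two-stage Kaplan-Meier simulation with a log(-log) z-test and entry at month 3 gives 82.2%. Both are within two points of 84%. The same simulation on the plain scale gives 89.9%. The documents do not name the scale; log(-log) is used below.

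**Assumptions not in the documents.** A share f of patients who would progress by month 12 switch one month before progression would have been documented, and survive to month 12. The values f = 5%, 10% and 20% are illustrative. There are 4,000 runs per setting and no futility stop. At a rejection rate near 10%, the Monte Carlo standard error is √(0.1 × 0.9 / 4000) = 0.5 points.

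**Closed-form check of the estimate.**
- Last contact (2.2): the switched share never counts as an event, so S = 1 − 0.46(1 − f). This gives 0.563, 0.586 and 0.632.
- Censored at the switch (a close reading of 8.2.1/8.2.5): the observed hazard falls by the factor 1 − f, so S = 0.54^(1 − f). This gives 0.557, 0.574 and 0.611.

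**Simulation at the null, switching that anticipates progression (mean KM; rejection).**

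| f | Last contact (2.2) | Censored at switch | Switch counted as event |
|---|---|---|---|
| 0 | 0.542; 4.2% | 0.542; 4.2% | 0.542; 4.2% |
| 5% | 0.564; 7.4% | 0.557; 6.8% | 0.536; 4.0% |
| 10% | 0.585; 11.4% | 0.573; 9.1% | 0.530; 3.2% |
| 20% | 0.628; 27.7% | 0.605; 19.8% | 0.520; 3.2% |

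Repeating the simulation moves the rejection rates by up to about one point, hence the rounded ranges in the conclusion. On the plain scale all rates are higher: at f = 10%, 17.8% under last contact and 13.2% when censored at the switch, against 7.1% without switching.

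**Switching unrelated to progression, 20% switching by month 12** (without switching: 0.540; 4.4%).
- Last contact: 0.580; 11.0%.
- Censored at switch: 0.541; 4.4%.
- Switch counted as event: 0.429; 0.2%.

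The 2.2 rule is therefore biased upward with or without informative switching. Censoring at the switch is biased only when switching is informative. Counting the switch as an event is strongly conservative when switching is unrelated to progression, so it is better suited to a sensitivity analysis than to the primary rule.

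**Does censoring at the last assessment remove informative censoring?** With 56-day assessments, f = 10% gives 0.572 and 10.1% (censored at the switch in the same simulation: 0.573 and 10.1%). At f = 20% it gives 0.605 and 19.5% (against 0.608 and 19.4%). It does not.

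**The case against.** Five points can be made for the plan.

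- Both statistical sections already use the better date, and even 2.2 applies its rule to patients last known to be progression-free. A reader might infer that the plan as a whole credits unassessed time. It does not: that follows only from the literal date in 2.2. But 2.2 is the endpoint definition, and nothing says which section prevails.
- A reader might infer that only survival is collected after a switch. Footnote 19 suggests so, but section 5.8 refers to survival and follow-up data without saying what the latter contain. What stands is that no disease evaluation is scheduled after a switch. Deaths after a switch remain PFS events under every wording.
- A reader might conclude that both rules inflate PFS in any case. The working shows otherwise for censoring at the switch. That early switchers are close to progression is plausible, but nothing in the documents establishes it.
- Switching may be rare. Serum markers are checked every cycle, three-monthly follow-up continues after early discontinuation, and concomitant anticancer therapy is prohibited (5.6). Nothing in the documents supports 20% or any other share.
- How the source of the 54% benchmark handled new therapy is not stated, so the net effect on the comparison with 54% cannot be determined from the documents.

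The simulations in 8.2.3 do not settle the matter. They cover up to 10% censoring but do not say whether that censoring was related to progression.

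**Conclusion.** The censoring dates in 2.2 and in 8.2.1/8.2.5 conflict, and none of these sections says what happens at new anti-myeloma therapy before documented progression. Under 2.2 read literally, 12-month PFS is biased upward even by unrelated switching. Under 8.2.1/8.2.5, read as ending credit at the last disease assessment, bias needs switching that anticipates progression.

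For assumed shares of 5% to 20%, the null estimate rises by about 2 to 9 points under 2.2 (0.564 − 0.542 to 0.628 − 0.542). With censoring at the switch it rises by about 1.5 to 6 points (0.557 − 0.542 to 0.605 − 0.542). One-sided rejection goes from about 4% to about 7–8%, 11% and 28–29% under 2.2, and to about 7%, 9–10% and 20% when censored at the switch.

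These sizes depend wholly on the assumed share, the one-month lead, survival to month 12 after the switch and the log-log scale. They show sensitivity and do not predict this trial's error rate. The conflict itself rests on the text alone.

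**What to change.** 1. Replace last contact in 2.2 so that 2.2, 8.2.1 and 8.2.5 all censor at the last adequate disease assessment showing no progression.
2. Record the start date of any new anti-myeloma therapy on the case report form.
3. Pre-specify a sensitivity analysis that counts new anti-myeloma therapy before documented progression as an event. This is needed because step 1 removes the unassessed credit but not informative censoring.
4. If progression dates after a switch are abstracted from routine records, use them only in a labelled supportive analysis, so that the primary estimand stays clear.

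The cost is wording in three sections, one recorded date and one extra analysis. The reported estimate may be slightly lower. Treatment and visit schedules do not change.

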#### 2.3 Secondary Objectives

- 1. To describe the toxicity profile of belantamab mafodotin given as maintenance after CAR-T.
- 2. To describe progression-free survival.
- 3. To describe changes in IMWG response for patients not in CR when initiating therapy with

- belantamab mafodotin as post-CAR-T maintenance.
- 4. To identify the rate of elimination of MRD ( $<10^{-5}$ ) in patients with myeloma at baseline and after starting belantamab mafodotin as post-CART maintenance (at screening/baseline, and after two, six, and 12 cycles).
- 5. Patient-reported quality of life studies (QoL).
- 6. To describe the overall survival for the entire cohort from the time of CAR-T administration.

#### 2.4 **Secondary Endpoints**

- 1. Best objective response on the trial (by IMWG criteria).
- 2. Progression-free survival.
- 3. Negative MRD ( $\leq 10^{-5}$ , by clonoSEQ®), including imaging plus MRD-negativity ( $\leq 10^{-5}$  in bone marrow and no area of PET-CT FDG uptake greater than mediastinal blood pool or surrounding normal tissue.
- 4. Duration of response on maintenance.
- 5. Time to progression/relapse after CAR-T.
- 6. Overall survival for the entire study population.
- 7. Adverse events on the trial.
- 8. QoL parameters.

#### 2.5 Exploratory Objectives

1. Exploratory: myeloma cell BCMA expression by flow cytometry and BCMA/BAFF/APRIL levels will be monitored (at baseline, two, six, and 12 cycles).

#### 2.6 Exploratory Endpoints

1. Baseline and on-treatment sBCMA/BAFF/APRIL and BCMA expression on myeloma cells.

#### 3 STUDY DESIGN

#### 3.1 General Description

This is a multicenter phase II, open-label study evaluating the efficacy and safety of belantamab mafodotin maintenance in participants with RRMM who have received commercially available anti-BCMA CAR-T cell therapy.

Subjects will be screened and enrolled 60-120 days after anti-BCMA CAR-T and receive belantamab mafodotin as maintenance therapy. Each maintenance cycle will have a duration of 56 days (+/- three days) and belantamab mafodotin will be administered at a dose of 1.9 mg/kg IV on day 1 of each cycle.

The study will include a screening period, central eligibility confirmation, a treatment period, and a followup period. During the 30-day screening period, participants will be evaluated for study eligibility per protocol as defined in the inclusion/exclusion criteria. Eligible participants must have a confirmed diagnosis of MM, been previously treated with anti-BCMA CAR-T cell therapy and have achieved at least SD, and not achieved CR/sCR. Following screening, central eligibility confirmation occurs and participants will be started on maintenance therapy within 90-120 days after receiving CAR-T cell therapy. Subjects will be enrolled in the trial within 30 days of screening procedures (consent not included) and start treatment within the 90-120 days window after anti-BCMA CAR-T.

Short Title: MCW EMBRACE TRIAL Version No.: 3 During the treatment period, subjects will receive belantamab mafodotin as maintenance therapy. Each treatment cycle will have a duration of 56 days (i.e., eight weeks +/- three days). Safety and disease assessments will be performed regularly according to the Schedule of Activities.

For all subjects, disease evaluations will continue to be performed at least every 56 days (± seven days) until confirmed PD, death, start of a new anti-cancer treatment, withdrawal of consent, or loss to followup, whichever occurs first. Traditional efficacy assessment will be performed every cycle by serum protein electrophoresis and immunofixation and serum-free light chains, and after every two cycles by 24-hour urine protein electrophoresis and immunofixation. Minimal residual disease (MRD) assessment by next generation sequencing (clonoSEQ®), BCMA expression on bone marrow plasma cells and soluble BCMA/BAFF/APRIL will occur at screening and after two, six, and 12 cycles of belantamab mafodotin maintenance (refer to correlative schedule). In case of PD, subjects will be followed to ascertain subsequent anti-cancer therapy, if any, and survival status every six months (± 30 days) until withdrawal of consent, lost to follow-up, death, or the end of the study. Patients who discontinue treatment prior to progression will continue standard-of-care follow-up every three months until progression or start of another treatment (whichever comes first), then they will continue to long-term follow-up.

#### 3.2 Study Population

Adult patients with myeloma who are within 90-120 days after receiving BCMA-directed CAR-T as standard of care for relapsed/refractory myeloma and having received at least four prior lines of therapy (including a PI, IMiD and anti-CD38 monoclonal antibody) before CAR-T.

#### 3.3 Estimated Time for Completion of Study Enrollment

The study will reach primary enrollment completion in approximately 24 months from the time the study opens to accrual.

#### 3.4 Estimated Time for Study Completion

The study will reach study completion in approximately nine years (four years for completion of treatment for all patients, and five years of long-term survival follow-up) from the time the study opens to accrual.

### 4 SUBJECT PARTICIPATION, DISCONTINUATION AND WITHDRAWAL

The MCW sIRB is the IRB of record for all participating sites. All sites must follow MCW sIRB requirements and policies regarding subject participation, found here:

https://www.mcw.edu/HRPP/Policies-Procedures.htm

#### 4.1 Subject Status

Subject statuses throughout the trial are defined as follows:

- Prescreening: preconsent (subject considering trial or study staff considering patient for the trial per institutional recruitment methods).
- Screening: period after consent, but prior to eligibility confirmation.

Short Title: MCW EMBRACE TRIAL Version No.: 3 Version Date: 12/29/2022

- Consented: consented, prior to eligibility confirmation.
- Eligible: the local investigator confirms all eligibly criteria apply.
- On study/enrolled: date eligibility is confirmed.
- On arm: date of enrollment.
- On treatment: first day treatment was given to the last day treatment was given.
- Off treatment: the last day treatment was given.
- Off arm: the last day treatment was given.
- On follow up: from last day of treatment to the end of follow-up period.
- Off study: follow-up period completed, with no additional data gathered.
- Withdrawn: subject fully withdraws consent (i.e., refuses ALL follow-up, even survival) or is taken off study by the local PI.

#### 4.2 Prescreening and Screening Log

The MCW study PI regularly reviews screen failure reasons to understand barriers to accrual and consider amending eligibility criteria. Screen failures are defined as participants who were considered for the trial to participate in the clinical trial with or without consent but are not subsequently assigned to the study intervention or enrolled in the study.

Prescreening/screening logs are maintained at each site and provided deidentified to MCW upon request.

#### 4.3 Consent

Investigators or their designees will identify potentially eligible subjects from their clinics, subject selfreferrals, referrals from other clinicians, and/or other sIRB-approved recruitment methods. No study conduct, including subject screening, can occur until after sIRB initial study approval and an official activation letter.

A written, signed informed consent form (ICF) and a Health Insurance Portability and Accountability Act (HIPAA) authorization (as applicable) must be obtained before any study-specific assessments are initiated.

After consent, the following occur:

- The site should email the MCW Multisite Team email as soon as possible.
- An OnCore® new subject entry must occur within 24 hours of consent.
- A case/subject/sequence number is assigned in OnCore® from the site in sequence (i.e., inputted from the site staff, not generated by OnCore®).
- Sites enter the case number according to the following template "Site-EMBRACE-001" (unless otherwise specified by the MCW Multisite Team), where "site" is an abbreviation of the site name (e.g., MCW), EMBRACE indicates the trial, and "001" is the sequential subject who consented to the trial at the site (e.g., the first consented subject at MCW would MCW-EMBRACE-001).

#### **4.4 Screening Procedures**

Refer to the study calendar of events.

Visit procedures that were performed as standard of care prior to consent (without the specific intent to make the subject eligible for the trial), may count toward screening tests and eligibility if they are within the screening window.

#### 4.5 Central Eligibility Confirmation

Short Title: MCW EMBRACE TRIAL 30 Version No.: 3 Central eligibility confirmation occurs in the following manner:

Participating sites prepare eligibility documents.

- The local PI or designated sub-investigator must review and sign/date (or confirm via email) the eligibility criteria section.
- It is highly recommended that participating sites include written dates and/or values of procedures next to all criteria on the right margin of the page (e.g., 'ECOG score is 0 on date 01/01/1900).
- Subject initials and study case/sequence number should be written on each page of the eligibility pages and supporting source documents — all of which must be deidentified.
- Supporting source documents are required for all item's eligibility criteria (i.e., pathology report, prior therapy history, age, consent, etc.), consent, and documentation of consent process (with key information highlighted or circled if possible, to aid in auditing and quick central eligibility confirmation).

#### Central Eligibility Confirmation

- The eligibility documents required above should be uploaded into the shared study folder (site folder access shared by the MCW Multisite Team) or emailed, and sites should notify the MCW Multisite Team email and MCW PI via email of completion. Participating site staff must inform the MCW PI if the MCW Multisite Team email returns an out-of-office email reply. If sites have an issue uploading into Box, emailed documents will suffice until the issue is resolved. MCW eligibility confirmation may occur via email if a physical signature would significantly delay enrollment.
- The MCW PI or MCW sub-investigator, with the assistance from the MCW Multisite Team, will review, request additional information, and confirm subject eligibility within approximately one business day of receipt of documents via email (Monday through Friday, excluding holidays. Sites must email the MCW Multisite Team prior to a Friday enrollment or holiday.)
- Eligibility criteria within a timeframe of "enrollment" means central eligibility confirmation from MCW (not the local investigator). Sites must ensure the one business day window for central confirmation does not put an eligibility procedure outside of the required time window. If this is potentially an issue, sites should notify the MCW Multisite Team email and MCW PI with supporting documents prior to intended enrollment date.

\*Note (for MCW only): After signoff from the MCW enrolling investigator, MCW staff should provide the MCW Multisite Team central eligibility documents for their review and clarification/documentation requests. The MCW study PI (or Study Chair) will then sign off (or confirm via email) for central eligibility confirmation (if they are unavailable, another MCW designee who is not the local enrolling investigator may sign off). If the enrolling investigator is the MCW study PI, MCW staff should provide the MCW Multisite Team signed central eligibility documents for their review and clarification/documentation requests, then the Study Chair (or vice versa study PI) will sign off (or confirm via email) for central eligibility confirmation (if they are unavailable, another MCW investigator may sign off, unless that is not possible).

Short Title: MCW EMBRACE TRIAL Version No.: 3 31

Subject Initials:	Subject Study ID:
Enrolling physician signature:	Date:

